The primary endpoint of this study is the **length of morphine sulfate therapy** ~~time from initiation of adjunctive therapy until hospital discharge in the two groups~~. Secondary end points include **time from initiation of adjunctive therapy until hospital discharge in the two groups**, length of stay, ~~length of morphine sulfate therapy~~, percentage of patients requiring triple therapy, safety and readmission rates.

Number of subjects

Approximately 50 patients will be enrolled in the study.

Inclusion / Exclusion Criteria

Inclusion Criteria

Infants greater than or equal to 35 weeks admitted to the neonatal intensive care unit (NICU) who have failed monotherapy with morphine sulfate will be eligible for enrollment in the study. Infants considered to have failed morphine sulfate therapy are those whose dose exceeds 0.15 mg (0.4 mL) q3h or have failed two attempts at weaning after initial stabilization.

Exclusion Criteria

Infants who develop NAS due to iatrogenic causes (analgesia or sedation), are unable to take oral medications at any point during their treatment or are in the custody of the department of child protective services with no legal guardian identified at the time of enrollment will be excluded.

Recruitment Methods

Subjects will be identified through medical record screening, contact with investigators patients in the clinical setting and referral from non-investigators (physicians, nurse practitioners or physician assistants).

Consent process

- An informed consent will be obtained from the parent or legal guardian for all infants enrolled in the study.
- A notice of research will be provided with the admission documents to the parent/legal guardian of all infants being admitted for NAS. If the patient fails monotherapy, the informed consent interview will be conducted and consent obtained over the phone. The full signed consent will be left at the patient bedside and given to the parent/legal guardian at their next visit to the hospital.

- The informed consent interview will be conducted over the phone by study personnel if the legal guardian is not present at the time it is determined that an adjunctive agent is needed to control the study participants' symptoms of NAS. Documentation of consent by the legal guardian will be noted by the study investigator and a witness. A copy of the informed consent will be left at the subject bedside to be provided to the legal guardian at the next visit to the NICU.

Methodology

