Study Design

This study will be a prospective, single-site, randomized, open-label study with institutional review board (IRB) approval. The study will be conducted in the neonatal intensive care unit (NICU) at the University of Tennessee Medical Center.

Study Treatment

Infants who have failed monotherapy with morphine sulfate and have documented informed consent will be randomized to receive phenobarbital (20 mg/kg load, then 5 mg/kg/day divided q12h) or clonidine (6 mcg/kg/day divided q3h). The phenobarbital and clonidine suspensions are 4 mg/mL and 10 mcg/mL, respectively. Study agents will be titrated to achieve control of symptoms (previous 24-hour average FS less than or equal to 8). The phenobarbital dose will be adjusted to obtain a desired trough of 25 to 30 mcg/mL. Levels will be obtained on Day 6, then weekly thereafter. Infants with a trough less than 25 will receive an adjusted load of phenobarbital 1 mg/kg for every 1 mcg/mL increase from obtained level to achieve a desired level of 25 mcg/mL and a change in the maintenance dose using a ratio of desired to measured phenobarbital level. Clonidine will be escalated by 1.5 mcg/kg/day every 24 hours (maximum 12 mcg/kg/day) to achieve control of symptoms. Blood pressure (BP) is documented prior to each clonidine administration. If hypotension occurs while receiving clonidine, the current dose will be held. If more than 2 clonidine doses are held in the previous 24 hours the total daily dose will be decreased by 1.5 mcg/kg/day. After control of symptoms, morphine sulfate will be weaned by 0.02 mg (0.05 mL) every 24 hours as tolerated until off. Morphine sulfate will be weaned if symptoms are controlled, and no rescue doses are required in the previous 24 hours. A rescue dose of morphine sulfate 0.02 mg (0.05 mL) may be given every 3 hours for consecutive FS greater than or equal to 11 while morphine sulfate is being weaned and after discontinuation. Infants who experience return of symptoms and require more than 2 rescue doses in the preceding 24 hours after discontinuing morphine will be placed back on the 0.02 mg (0.05 mL) until symptoms are controlled. Once symptoms are again controlled, a second attempt to discontinue morphine sulfate will occur. After morphine sulfate has been discontinued for 24 hours and symptoms are still controlled, the study agent can be weaned. Clonidine will be weaned by 25% (based on the dose at time of morphine sulfate discontinuation) every 24 hours over 72 hours. Infants will be observed for return of symptoms and rebound hypertension for 48 hours prior to discharge. Blood pressure will be measured every shift for 48 hours after discontinuation of clonidine. Infants who experience rebound hypertension or fail to maintain control of symptoms after

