
discontinuation of clonidine will be placed back on the last effective dose until symptoms are controlled. Once symptoms are controlled, weaning will resume. Infants receiving phenobarbital will also be observed for 48 hours after the discontinuation of morphine sulfate prior to discharge. Phenobarbital will be weaned as an outpatient based on the standard taper used in the NICU for over 5 years (Table 1).

Table 1: Standard phenobarbital taper based on dose at discharge

Phenobarbital dose on day of discharge	Standardized phenobarbital taper initiated upon discharge
5.1 to 7 mg every 12 hours	6 mg two times a day for 1 week, then 4 mg two times a day for 1 week, then 2 mg two times a day for 1 week, then 2 mg once a day for 1 week, then stop
7.1 to 9 mg every 12 hours	8 mg two times a day for 1 week, then 6 mg two times a day for 1 week, then 4 mg two times a day for 1 week, then 2 mg two times a day for 1 week, then stop
9.1 to 11 mg every 12 hours	10 mg two times a day for 1 week, then 8 mg two times a day for 1 week, then 4 mg two times a day for 1 week, then 2 mg two times a day for 1 week, then stop
11.1 to 13 mg every 12 hours	12 mg two times a day for 1 week, then 8 mg two times a day for 1 week, then 6 mg two times a day for 1 week, then 2 mg two times a day for 1 week, then stop
13.1 to 15 mg every 12 hours	14 mg two times a day for 1 week, then 10 mg two times a day for 1 week, then 6 mg two times a day for 1 week, then 4 mg two times a day for 1 week, then stop

If symptoms are unable to be controlled with the study agent alone, the addition of the nonrandomized medication (phenobarbital/clonidine) may be initiated to control symptoms. Morphine, clonidine and phenobarbital, in that order, will be weaned per protocol.

The patient medical record will be reviewed to collect data about the subjects. This includes the patient’s electronic medical record and chart.

Risks to subjects

Risks to participants include side effects associated with study medication, potential increased length of stay/treatment compared to those patients receiving comparative medication and loss of confidentiality. Both of the study medications are commonly used in this patient population and considered standard of care with no evidence of superiority in the treatment of NAS.

Benefits to subjects

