It is not known if one of the study medications will better control withdrawal symptoms, allow us to wean oral morphine faster, have fewer side effects or allow the infant to be

discharged from the hospital sooner. The knowledge gained from this research will help us determine if clonidine or phenobarbital could better control symptoms of withdrawal, have less side effects or allow children to be discharged from the hospital sooner.

Data Management

- The primary endpoint of time from initiation of adjunctive therapy until hospital discharge will be assessed using Mann-Whitney U test. Secondary Endpoints of length of stay and length of morphine therapy will also be assessed via Mann-Whitney U test. Side effects and readmission rate via chi-squared with an unadjusted odds ratio with 95% CI for 30-day readmission.
- A power analysis was completed for sample size (based on Surran et al findings with power to detect a 5-day difference in treatment time):

t tests – Means: Difference between two independent means (two groups)		
Analysis:	A priori: Compute required sample size	
Input:	Tail(s)	= Two
	Effect size d	= 3.0666667
	α err prob	= 0.05
	Power (1- β err prob)	= 0.80
	Allocation ratio N2/N1	= 1
Output:	Noncentrality parameter δ	= 4.3369216
	Critical t	= 2.4469119
	Df	= 6
	Sample size group 1	= 4
	Sample size group 2	= 4
	Total sample size	= 8
	Actual power	= 0.9475121

It is predicted that a sample size of 25 in each treatment group will be powered to detect 1.2-day difference in time from initiation of adjunctive therapy until hospital discharge.

- All paper research records containing data from individual subjects will be locked and stored. All electronic research records containing data from individual subjects will be computer password protected. All records will be accessible only to research personnel.

Withdrawal of Subjects

Subjects may withdraw their permission for participation in research at any time. Subjects will contact [name] in writing to let us know they are withdrawing their permission. □ The mailing address is [name]. □ At that time, we will stop further collection of any information. □ However, the health information collected before this withdrawal may continue to be used for the purposes of reporting and research quality.

References

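### Hospital-time endpoints that stop at discharge count relapse days on adjunct withdrawal mainly in the clonidine arm, so readmission days should be added in a companion endpoint

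*Combined protocol and SAP*

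**What the plan says.** **Endpoints.** Study Endpoints lists "time from initiation of adjunctive therapy until hospital discharge in the two groups" and length of stay as secondary, followed by "percentage of patients requiring triple therapy, safety and readmission rates". The first of these ends at discharge by its own wording. Length of stay has no start or stop definition. No text adds readmission days to either.

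**Analysis.** Data Management plans: "Secondary Endpoints of length of stay and length of morphine therapy will also be assessed via Mann-Whitney U test". It compares readmission by chi-squared with an "unadjusted odds ratio with 95% CI for 30-day readmission". The duration of a readmission enters no analysis. The same section still calls time from adjunct start to discharge the primary endpoint, although the revised Study Endpoints section makes length of morphine therapy primary.

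**Clonidine (Study Treatment).** "After morphine sulfate has been discontinued for 24 hours and symptoms are still controlled, the study agent can be weaned". Clonidine then comes down in steps "every 24 hours over 72 hours", with 48 hours of observation before discharge and blood pressure checks for 48 hours after the drug stops. The rule for rebound hypertension or loss of symptom control is that infants affected after "discontinuation of clonidine will be placed back on the last effective dose until symptoms are controlled". Weaning then resumes.

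**Phenobarbital (Study Treatment and Table 1).** Infants are observed for 48 hours after morphine stops and go home on the drug: "Phenobarbital will be weaned as an outpatient based on the standard taper". Every row of Table 1 has four one-week steps.

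**The concern.** Return of symptoms while the adjunct is being withdrawn is treated differently by the hospital-time endpoints in the two arms. On clonidine, withdrawal and the first 48 hours off drug take place before discharge, so a relapse lengthens the measured stay. On phenobarbital, withdrawal starts after the clock has stopped. A relapse then cannot lengthen the measured stay, and an infant discharged early and readmitted is scored as a short stay.

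Benefits to subjects says the trial should help show which drug gets infants out of hospital sooner. If relapse risk on withdrawal were the same in both arms, an index-stay comparison would still lean toward phenobarbital. The readmission analysis records that an infant came back but not for how long, so it cannot put those days back into the comparison.

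**Working it through.** **1. The plan's own figure.** The power output reproduces. With d = 3.0666667 and 4 per group, noncentrality = 3.0667 × √(4/2) = 4.337, critical t on 6 df = 2.447, and power = 0.9475. It contains no relapse or readmission input, so it does not settle this point.

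**2. Minimum hospital time after morphine stops, no relapse (Study Treatment).**
- Clonidine: 24 h + 72 h wean + 48 h observation = 144 h (6 days). If the 48 h is read as overlapping the wean, 24 + 72 = 96 h (4 days). The blood pressure rule, which runs from clonidine discontinuation, favours the longer reading.
- Phenobarbital: 48 h (2 days).
- Scheduled gap: 6 − 2 = 4 days, or 4 − 2 = 2 days. This exists without any relapse and is separate from what follows.

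**3. Extra shift from relapse.** Let p be the probability of relapse on adjunct withdrawal (the same in both arms), L the inpatient days per relapse, f the share of phenobarbital relapses after discharge, and g the share of clonidine relapses after discharge.
- Counted relapse days per infant: clonidine p × L × (1 − g); phenobarbital p × L × (1 − f).
- Shift toward phenobarbital = p × L × (f − g).

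The documents give none of these four inputs. With L = 5 days **assumed**:

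| p | g = 0, f = 50% | g = 0, f = 100% | g = 25%, f = 50% | g = 25%, f = 100% |
|---|---|---|---|---|
| 10% | 0.25 d | 0.50 d | 0.125 d | 0.375 d |
| 20% | 0.50 d | 1.00 d | 0.25 d | 0.75 d |
| 30% | 0.75 d | 1.50 d | 0.375 d | 1.125 d |

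Example: 0.30 × 5 × (1 − 0) = 1.50 days. With L = 3, g = 0 and f = 100%, the range is 0.10 × 3 = 0.3 to 0.30 × 3 = 0.9 days.

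**4. Effect on the Mann-Whitney test, by simulation.** Assumed: 25 per arm, gamma-distributed stays with mean 12 and SD 4 days, 5 days per relapse, no true drug difference.
- No scheduled gap, g = 0: index stay rejects in about 6–21% of trials over the p and f range above. With g = 25%, about 5–14%. With SD 8 and g = 0, about 5–11%.
- Scheduled gap alone, no relapse: about 40% at 2 days and 93% at 4 days.
- Scheduled gap plus relapse, total inpatient days as outcome: still about 30–90%.

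The last two lines show that the scheduled gap dominates, and that counting readmission days does not remove it.

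**The case against.** The strongest case against has five parts.

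- **Index-only counting is inferred for length of stay.** True. It is the natural reading, because readmission is listed separately, but the plan does not say so. For time to discharge it is the stated wording.
- **Time to index discharge is a legitimate quantity, and readmission is reported beside it.** This stands as a reason to keep both index measures. It does not make them sufficient for a conclusion about hospital time.
- **The asymmetry is not total.** Relapse soon after morphine stops adds days in both arms, and clonidine relapse beyond the 48 hours of observation goes uncounted as well. This stands and shrinks the shift, as the g = 25% columns show.
- **The inputs are assumed.** Equal relapse risk is supposed for a 72-hour wean and a 28-day taper, and 5 days per relapse wherever it occurs. This stands; the size is illustrative.
- **These are secondary endpoints.** This holds if Study Endpoints governs, but not if Data Management does.

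Three stronger readings are tempting, and the documents support none of them.

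- A reader might infer that the trial's false-positive rate rises to about 20% and that counting readmission days restores 5%. That holds only with no scheduled gap, which is not this protocol. The return to 5% is also built in by giving every relapse the same inpatient cost in both arms.
- A reader might set the shift against the planned 1.2-day difference. The scales differ. With 25 per arm, 80% power needs d = 0.809, so 1.2 days implies an SD of 1.2/0.809 = 1.48. At the SD of 4 assumed here, the detectable difference is 0.809 × 4 = 3.2 days.
- A reader might dismiss the readmission comparison as powerless. Power is low (about 3–23%) if 5–10% of phenobarbital infants and no clonidine infants return, but about 76–96% if 20–30% return. The limitation is that it ignores duration.

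**Conclusion.** The concern holds as a directional tilt of uncertain size. Relapse on adjunct withdrawal adds counted hospital days mainly on clonidine and largely drops out on phenobarbital, where it is seen only if it leads to readmission and then only as yes/no. Under the assumptions shown (10–30% relapse, 5 days each, every clonidine relapse before discharge, 50–100% of phenobarbital relapses after it), the shift is 0.25 to 1.5 days toward phenobarbital. It falls to roughly 0.1 to 1.1 days if a quarter of clonidine relapses also follow discharge. The direction requires only that a larger share of relapses fall after discharge on phenobarbital than on clonidine, given similar relapse risk and cost.

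This comes on top of the scheduled 2 to 4 day gap, which is the larger distortion and a separate point. Whether the primary endpoint is affected depends on reconciling Study Endpoints with Data Management.

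**What to change.** In Study Endpoints and Data Management:

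1. Define length of stay and time from adjunct start to discharge explicitly as index-admission measures, and keep both.
2. Add total inpatient days, index plus readmission, from adjunct start to one fixed day common to both arms, compared by Mann-Whitney. Set the day late enough to cover the outpatient taper. For illustration, an assumed 12-day stay plus the 28-day taper ends on day 40, so allowing for longer stays means a later day.
3. State that any conclusion about which drug reduces hospital time will rest on total inpatient days, not on index stay alone.
4. Record readmission dates and length in the chart review already planned.
5. Reconcile the two sections on which endpoint is primary.

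Nothing in treatment, weaning or discharge practice changes. The cost is one definition, a few chart fields, and chart review running somewhat past the 30-day readmission window (12 + 30 = day 42 in the same illustration). Readmissions to other hospitals may be missed, as they may be for the existing readmission endpoint. The scheduled wean gap remains in the new endpoint as real hospital time, so this change does not deal with that separate issue.

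### Side effects are compared with no stated observation window, and the discharge rules leave the clonidine course fully charted but the 28-day phenobarbital taper at home without planned side-effect collection

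*Combined protocol and SAP*

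**What the plan says.** **Endpoint and test.** Study Endpoints lists among the secondary endpoints "percentage of patients requiring triple therapy, safety and readmission rates". Benefits to subjects names fewer side effects as one of the questions the trial should help answer. Data Management gives the whole side-effect analysis as "Side effects and readmission rate via chi-squared"; the line reads in full "Side effects and readmission rate via chi-squared with an unadjusted odds ratio with 95% CI for 30-day readmission". It states no start or end of side-effect collection and no allowance for time observed. The only time window in that line belongs to readmission.

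**Data source.** Study Treatment says "The patient medical record will be reviewed to collect data about the subjects", meaning the electronic record and chart. No visit, call or diary after discharge is described.

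**Clonidine.** "After morphine sulfate has been discontinued for 24 hours and symptoms are still controlled, the study agent can be weaned". Then "Clonidine will be weaned by 25% (based on the dose at time of morphine sulfate discontinuation) every 24 hours over 72 hours". Before going home, "Infants will be observed for return of symptoms and rebound hypertension for 48 hours prior to discharge", and blood pressure is taken every shift for 48 h after the drug is stopped.

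**Phenobarbital.** Infants are observed for 48 h after morphine is stopped and then discharged on the drug. The plan says "Phenobarbital will be weaned as an outpatient based on the standard taper used in the NICU for over 5 years (Table 1"). Each of the five rows of Table 1 has four one-week steps.

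**Both drugs.** An infant in either arm may be given the other drug if symptoms are not controlled. Phenobarbital is then weaned last.

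**The concern.** A chi-squared test on the proportion of infants with a side effect is a fair comparison only if both arms are watched for a comparable time and through comparable phases. Here the treatment rules separate them. Starting, weaning and stopping clonidine all happen in hospital, and rebound hypertension is looked for by name. Phenobarbital is started in hospital but weaned and stopped at home. Randomization does not remove this difference, because it comes from the treatment rules of each arm.

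At stake is the answer to a stated question. If side effects are taken from the chart as it stands, a difference between the arms may reflect how long and how closely the infants were observed and not the drugs themselves. A lack of difference could equally hide a real one.

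**Working it through.** The documents give no event rate, expected count or power figure for side effects, so there is no figure of the plan's own to reproduce on this point. The check is a timeline, followed by two illustrations on stated assumptions.

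**1. Charted time after morphine stops, if no step fails (Study Treatment)**

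| | Clonidine | Phenobarbital |
|---|---|---|
| Before the study agent may be weaned | 24 h | – |
| Inpatient wean | 72 h | none |
| Observation | 48 h off drug | 48 h from morphine stop, on drug |
| Total in hospital | 24 + 72 + 48 = 144 h = 6 days | 48 h = 2 days |
| Taper days after discharge (Table 1) | 0 | 4 × 7 = 28 |

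The inpatient gap is 6 − 2 = 4 days. None of the 28 phenobarbital taper days is in hospital.

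**2. What could catch an event during the taper.** One route is readmission within 30 days. If counted from discharge, which the plan does not say, this spans the 28-day taper. The other is any later entry that happens to be in the record. Neither is systematic for milder events at home.

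**3. Illustration of the inpatient gap alone.** Assumptions, none from the documents: 10 inpatient days on the adjunct before morphine stops in both arms, a constant and equal daily risk p, and capture until discharge only. Clonidine is then observed for 10 + 6 = 16 days and phenobarbital for 10 + 2 = 12. The expected proportion with any side effect is 1 − (1 − p)^days.

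- p = 0.02: 1 − 0.98^16 = 27.6% against 1 − 0.98^12 = 21.5%, a gap of 6.1 points.
- p = 0.05: 1 − 0.95^16 = 56.0% against 1 − 0.95^12 = 46.0%, a gap of 10.0 points.

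At 25 per arm, exact enumeration of the uncorrected chi-squared test at 0.05 gives rejection in about 8% and 13% of trials respectively, against about 5 to 6% when the proportions are equal.

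**4. How fragile the direction is.** Keep everything else, but let the phenobarbital arm need 5 more days of morphine; 5 days is the treatment-time difference named in the power analysis. Phenobarbital is then observed for 15 + 2 = 17 days against 16.

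- p = 0.02: 1 − 0.98^17 = 29.1% against 27.6%.
- p = 0.05: 1 − 0.95^17 = 58.2% against 56.0%.

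The sign reverses.

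**5. Illustration of the uncharted taper.** Assumptions: equal whole-course risk P in both arms, constant hazard over the phenobarbital course, inpatient-only capture, and 7 to 28 inpatient phenobarbital days. The charted share of the phenobarbital course is f = days/(days + 28), which is 7/35 = 0.20 to 28/56 = 0.50. The observed phenobarbital proportion is 1 − (1 − P)^f.

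- P = 20%: clonidine 20%, phenobarbital 4.4% (f = 0.20) to 10.6% (f = 0.50). Chance of a false significant difference at 25 per arm, by normal approximation: 39% to 15%.
- P = 30%: clonidine 30%, phenobarbital 6.9% to 16.3%. Chance 56% to about 20%.

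The two illustrations differ widely because they rest on different assumptions. That is why neither can be read as an estimate of the bias in this trial.

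**The case against.** The strongest reply is that the plan has an undefined window, not a biased one, and that a reader might infer more than it says in four ways.

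- **That collection stops at discharge.** No section says so. The record is not limited to the index admission. Inpatient-only capture is an inference from the data source and the absence of follow-up contacts. This objection stands.
- **That taper events can be recorded only for clonidine, or that the taper is omitted altogether.** This is too strong. Readmission within 30 days can catch the events serious enough to bring the infant back, and later chart entries may exist. Ascertainment is passive and incomplete, but not absent.
- **That the comparison must favour phenobarbital.** This needs equal constant risk and equal time to morphine stop. Phenobarbital begins with a load and later tapers down, while clonidine may be escalated in hospital, so flat risk is not given. Time to morphine stop also drives the current primary endpoint, so assuming it equal assumes no efficacy difference. Step 4 shows the sign can reverse.
- **That the split is exactly by arm.** A clonidine-arm infant given phenobarbital as well has phenobarbital weaned last and may also go home on the taper.

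The Background also names concerns for both drugs: hypotension and rebound hypertension for clonidine, neurodevelopment and alcohol exposure for phenobarbital. It does not single out one.

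The objection does not remove the difference in observation. The discharge rules are explicit, no collection at home is planned, and the only test is a crude proportion. Carrying out the plan as written therefore gives unequal ascertainment on a stated question, which goes beyond a missing detail.

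**Conclusion.** The concern holds in a limited form. With no window stated and chart data as the source, the charted period includes the whole clonidine course, its wean and 48 h off drug (about 6 days after morphine stop). For phenobarbital it includes only 48 h after morphine stop, and the 28 taper days have no planned side-effect ascertainment beyond 30-day readmission and incidental entries. Crude proportions over such periods cannot by themselves show which drug has fewer side effects.

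The 6-day, 2-day and 28-day figures follow from the documents, provided that no wean fails and no infant receives both drugs. The direction and size of any bias do not follow from them. The 6 to 10 points and the false-positive chances above are illustrative only. The matter should be corrected before analysis; it concerns a secondary endpoint and leaves the primary comparison untouched.

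**What to change.** In Data Management:

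1. Make the between-arm side-effect comparison, by randomized arm, over the phase that both arms complete in hospital: first adjunct dose to 48 h after the final morphine stop. The word final matters, because morphine can be restarted and stopped again.
2. Beside the proportions, report observed days per arm and events per patient-day, because the length of this phase depends on morphine duration and may differ between arms.
3. Report later events descriptively by phase, with no between-arm test: the clonidine wean and the 48 h after it, including rebound hypertension; and the phenobarbital taper, from readmission or outpatient chart entries. Identify infants who received both drugs.
4. State that the safety conclusion is limited to the inpatient phase and that taper-phase safety is not systematically assessed.

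The cost is wording, plus the dates of events and of the final morphine stop from the chart. Treatment and follow-up are unchanged. There are two downsides. Clonidine wean-phase events are reported but not tested against phenobarbital. Because the wean may begin 24 h after morphine stops, its first day can fall inside the shared phase, and the report should say so.
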